8.4.4 EVENTS OF SPECIAL INTEREST

Not applicable to this study.

8.4.5 REPORTING OF PREGNANCY

If the subject or partner of the subject becomes pregnant, the pregnancy is to be followed until the outcome is known. An IRB-approved Pregnant Subject or Pregnant Partner Data Release Form should be completed by the subject or the subject's pregnant partner in order to obtain consent to follow the progress of the pregnancy and birth, and the health of the infant.

Pregnancy is not considered an AE; however, any pregnancy will be collected on a Samumed Pregnancy Report Form. Information will be collected for any pregnancy in a female subject or the pregnant female partner of a male subject (if consenting), which occurs during the study, including perinatal and neonatal outcome. Infants resulting from such pregnancies should be followed for a minimum of 12 weeks.

8.5 STUDY HALTING RULES

Not applicable to this study.

8.6 SAFETY OVERSIGHT

Clinical safety oversight will be performed by centralized review conducted by Medical Monitors per the Medical Monitoring Plan. In addition, on-site review will be conducted by Clinical Research Associates.

9. CLINICAL MONITORING

All aspects of the study will be monitored by the Sponsor or the Sponsor's designees with respect to current Good Clinical Practice (GCP) and Standard Operating Procedures (SOPs) for compliance with applicable government regulations. It is the responsibility of the Investigator to provide all study records, including eCRFs and source documents among other records, for review and inspection by the clinical monitor.

Clinical monitoring will be performed per the Clinical Monitoring Plan. Clinical monitors will periodically evaluate the progress of the study, including the verification of appropriate consent form procedures and the verification of the accuracy and completeness of eCRFs. Clinical monitors will also ensure that all protocol requirements, applicable US FDA regulations, other regulatory requirements, and the Investigator's obligations are being fulfilled.

Centralized data monitoring will be performed per the Centralized Data Monitoring Plan in order to periodically evaluate study progress and risks. A regular report of risks will be utilized together with on-site and off-site centralized data monitoring to direct overall monitoring focus and activities to the areas of greatest risk which have the most potential to impact subject safety and data quality.

The accuracy of the data will be verified by reviewing the documents described in [Section 11](#).

10. STATISTICAL CONSIDERATIONS

10.1 STATISTICAL AND ANALYTICAL PLANS

This section describes the planned statistical analyses in general terms. A complete description of Phase A statistical analyses will be specified in a statistical analysis plan (SAP). A second SAP will be prepared for Phase B analyses.

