10.4.4 ANALYSIS OF PHASE B ENDPOINTS

Phase B endpoints will be analyzed in a similar fashion as Phase A endpoints. A separate SAP will be prepared for Phase B analyses.

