10.4.7 PLANNED INTERIM ANALYSES

This safety study was initially designed as a one-year double-blind study. The protocol was amended to add a built-in, one-year single blind extension (Phase B) after the formal, one-year core study (Phase A) completes. The primary analysis will be after last subject completes Week 52 in Phase A and should not be considered an interim analysis.

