10.6 MEASURES TO MINIMIZE BIAS

10.6.1 BLINDING PROCEDURES

Phase A is a double-blind study. Study medication will be provided to the investigational center. The investigational center must identify unblinded personnel who are able to prepare and perform the injection of study medication and/or placebo. Study personnel administering or preparing study medication and reference therapy must minimize any contact with the subject following the injection and may not perform any study assessments throughout the duration of the study. Each site will be required to document a blinding plan that identifies the blinded and unblinded personnel at the investigational center and describes how the study blind will be maintained.

Subjects will be assigned a subject number at their Screening Visit 1. On Day 1, eligible subjects will be randomized via the Medidata Rave database. Upon randomization of a subject, a Dispensation email will be sent from [contact] to the designated unblinded investigational staff member(s). Subjects will be randomized 1:1 (0.07 mg active per 2 mL injection : 2 mL placebo) to each treatment group using a permuted block design. Specific information regarding the use of Medidata Rave RTSM to store and implement the permuted block design will be detailed within the SAP.

Primary analysis of Phase A data will be completed after the last subject completes Week 52 (EOSa). While the Sponsor will be unblinded to study treatment after the Phase A analysis, the Investigator and the subject will remain blinded.

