Exclusion criterion #18 was edited to: “History of mania, bipolar disorder, psychotic disorder, schizophrenia, schizoaffective disorder, major depressive disorder, or generalized anxiety disorder”	Protocol Summary, Section 5.2	Change was made to refine exclusion criteria
Exclusion criterion #19 was edited: “...any experimental therapeutic procedure for knee OA within 26 weeks prior to Screening Visit 1...” is excluded.	Protocol Summary, Section 5.2	Change was made to refine exclusion criteria
Exclusion criterion #22 was edited to clarify systemic as “(oral, intramuscular, or intravenous)”.	Protocol Summary, Section 5.2	Change was made to clarify what constitutes systemic glucocorticoids
Study and participant durations were updated.	Protocol Summary	Change was made to reflect addition of Phase B
Schematic of Study Design was updated.	Schematic of Study Design	Change was made to reflect addition of Phase B
Risks associated with radiographs, qCT, and DXA were updated to reflect the additional imaging assessments performed in Phase B.	Section 2.3.1	Change was made to reflect the new number of imaging assessments to be performed
Where applicable, “Week 52 (EOS)/ET” was changed to “last study visit” (e.g., guidelines on	Sections 5.3.1, 7.1.1, 7.5.1	Change was made to clarify that these instances refer to the subject’s last

Change	Sections Affected	Rationale
contraception).		study visit, whether that be in Phase A or Phase B
Clarification and further guidelines were added to Section 5.3.1 Contraception.	Section 5.3.1	Changes were made to refine lifestyle guidelines pertaining to contraception
Edits were made to indicate that subjects who are withdrawn from study medication for safety reasons will continue with all planned study visits per protocol.	Sections 5.5.1, 5.5.2, 6.1.9	Change was made to follow subjects for safety despite withdrawing from study medication
Further information regarding injections was added to Section 6.1.5.	Section 6.1.5	Change was made to provide further guidance on IA injections
Study Procedures and Schedule were updated to include Phase B assessments and visits. Schedule of Events and Schedule of Electronic Diary and Questionnaire Completion tables were also revised.	Section 7	Change was made to reflect addition of Phase B
The following was added to Section 10.1: “A second SAP will be prepared for Phase B analyses and finalized prior to the Week 104 data lock.”	Section 10.1	Change was made to reflect addition of Phase B

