4.3 Treatment Blinding

Phase A of the study was double-blind. Study medication was provided to the investigational center, and the center identified unblinded personnel who were able to prepare and perform the injection of study medication and/or placebo. Study personnel administering or preparing study medication and reference therapy were to minimize any contact with the subject following the injection and not perform any study assessments throughout the duration of the study. Each site was required to document a blinding plan that identified the blinded and unblinded personnel at the investigational center and described how the study blind will be maintained.

Primary analysis of Phase A data was completed after the last subject completed Week 52 (EOSa). While the Sponsor was unblinded to study treatment after the Phase A analysis (after the last subject completed Week 52 [EOSa]), the Investigators and the subjects remained blinded for Phase B.

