9.2 Protocol Deviations

A protocol deviation is defined as any noncompliance with the clinical trial protocol requirements. The noncompliance may be either on the part of the subject, the Investigator, or the study site staff.

Deviations are summarized into one of the following categories:

- Investigational Product
- Informed Consent
- Enrollment
- Procedures
- Labs/Specimens
- Study Visits
- Source Documentation

- Diaries, Questionnaires, or Patient Reported Outcomes
- Subject Non-Compliance
- Serious Adverse Events

Deviations are categorized as major or minor by a cross-functional team according to pre-defined criteria established in the Protocol Deviation Classification Guideline.

- A major deviation is defined as a divergence from the protocol that materially (a) reduces the quality or completeness of efficacy data, (b) makes the informed consent inaccurate, or (c) impacts a subject's safety, rights or welfare.
- A minor deviation is defined as a divergence from the protocol that deviates from the procedures and guidelines outlined in the protocol, but is not classified as a major deviation (i.e. the deviation does not materially (a) reduce the quality or completeness of the data, (b) make the informed consent inaccurate, or (c) impact a subject's safety, rights or welfare).

Protocol deviations may result in subject exclusion from the PPASB. Prior to Phase B database lock, all protocol deviations were reviewed by study team members to determine if the deviation could reasonably affect/confound interpretation of efficacy endpoints and should result in the subject being excluded from the PPASB. Subjects with the following types of deviations were excluded from the PPASB:

- Subjects taking pain medications that may significantly impact pain and function assessment

A final list of protocol deviations resulting in subject exclusion from the PPAS and PPASB can be found in [Appendix 2](#).

Major protocol deviations that occurred in Phase B will be summarized by site and category, and all protocol deviations will be listed for each subject. Additionally, the COVID-19 pandemic related protocol deviations that occurred in Phase B will be summarized separately.

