12 EFFICACY ANALYSIS

A statistical description of Pain NRS at baseline will be provided along with absolute changes from baseline at each subsequent timepoint for subjects in the FASB and PPASB. Statistical descriptions of WOMAC Pain, WOMAC Function, Patient Global Assessment, and mJSW at baseline will also be provided along with absolute changes from baseline at each subsequent timepoint for subjects in the FASB only.

Changes in the target knee from baseline in Pain NRS will be characterized using MMRM for subjects in the FASB and PPASB; the models will be evaluated through Week 104 (EOSb). All models will use treatment group, week, treatment×week interaction, and baseline values as covariates. Unadjusted 95% confidence intervals and P values will be reported.

If a subject submitted data related to their non-target knee due to an electronic device error, this data will not be analyzed.

Subject-level listings will be provided.

Since Phase A analysis (defined prior to unblinding) was the primary analysis for this study, there will be no estimands provided for Phase B.

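### The Phase B SAP had no deadline before Sponsor unblinding, appears to have been finalised after it, and departs from the protocol's methods while declaring only one change

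*Protocol*

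**What the plan says.** **Timing of the SAP.** Protocol 10.1 states "A second SAP will be prepared for Phase B analyses" and Protocol 10.4.4 states "A separate SAP will be prepared for Phase B analyses". Neither attaches a milestone. Beyond that, 10.4.4 says only that Phase B endpoints are to be analysed similarly to those of Phase A.

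**Unblinding.** Protocol 10.6.1: "While the Sponsor will be unblinded to study treatment after the Phase A analysis, the Investigator and the subject will remain blinded". Protocol 10.4.7 adds that the Week 52 analysis "should not be considered an interim analysis".

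**The SAP's own position in time.** SAP 4.3 reports "While the Sponsor was unblinded to study treatment after the Phase A analysis", and SAP 5.1 reports the Phase A analysis as completed. SAP 12 states "Since Phase A analysis (defined prior to unblinding) was the primary analysis for this study, there will be no estimands provided for Phase B"; SAP 10 and 11 carry the same parenthesis, each time for Phase A only. SAP 9.2 describes the deviation review as done and says "A final list of protocol deviations resulting in subject exclusion from the PPAS and PPASB can be found in" an appendix.

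**Declared changes.** SAP 15 lists one: biomarker change is taken from baseline rather than from Week 52.

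**The concern.** SAP 8.1.1 keeps the Phase A baseline for Phase B, and the Phase B models run from that baseline to Week 104. The Phase A results by arm are therefore largely the first part of the series that the Phase B models analyse. If the Phase B models, analysis sets and contrasts are settled after those results are known, a reader cannot tell whether an analysis was kept, changed or dropped for neutral reasons. Secondary objective 3 covers effectiveness as well as safety from Week 52 to Week 104. The SAP reports unadjusted intervals and P values for Pain NRS, and least squares estimates, intervals and effect sizes for bone imaging. How far those can be relied on depends on when the methods were fixed.

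**Working it through.** **1. The plan's own figure.** The only computed design figure is the 81.6% power for a BMD ratio (Protocol 10.5, SAP 6). Inputs: CV 0.30, true ratio 0.93, limit 0.80, 50 per group, one-sided alpha 0.05.
- Log-scale SD = sqrt(ln(1 + 0.30²)) = 0.2936
- Distance = ln(0.93/0.80) = 0.1506
- Standard error = 0.2936 × sqrt(2/50) = 0.0587
- Noncentrality = 0.1506/0.0587 = 2.56 on 98 df
- Power from the noncentral t = 81.65%

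The figure reproduces. The point does not rest on it, but it shows that the sample size was built on the BMD ratio, which matters in step 4.

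**2. Order of events.** The protocol sets no SAP deadline and unblinds the Sponsor after the Phase A analysis, before Phase B ends. The SAP reports both the analysis and the unblinding as past, and says only of Phase A that it was defined beforehand. The SAP's final text therefore follows unblinding. Its date is not visible, so this rests on tense and content.

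**3. Share of each Phase B model's time points at or before Week 52** (weeks from SAP 11, 12, 13 and Appendix 1).

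| Model | At or before Week 52 | Total | Share |
|---|---|---|---|
| qCT, ANCOVA | 4 (12, 24, 36, 52) | 8 | 50% |
| DXA, ANCOVA | 2 (24, 52) | 4 | 50% |
| Pain NRS, MMRM | 52 | 104 | 50% |
| Biomarkers, ANCOVA | 5 (4, 12, 24, 36, 52) | 9 | 55.6% |

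Bone imaging and biomarkers use the SAS, so their Phase A visits are the same subjects' data. Pain NRS uses the FASB and PPASB, which require treatment in Phase B. For Pain NRS, the overlap with what was seen is large but not complete.

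**4. Protocol methods against the SAP.**

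| Item | Protocol 10.4.2-10.4.3 | Phase B SAP | Declared in SAP 15 |
|---|---|---|---|
| Target-knee BMD by qCT | MMRM, with ANCOVA as sensitivity analysis | ANCOVA only (8.1.2, 11) | No |
| BMD ratio with one-sided interval | Planned | Absent, though SAP 6 keeps it as the sample-size basis | No |
| WOMAC Pain, WOMAC Function, Patient Global Assessment, mJSW | MMRM | Descriptive only (12) | No |
| Durability models | MMRM from the Week 24 value | Absent, though durability is 5 of the 10 Phase B efficacy endpoints (3.2.7) | No |
| Pain NRS | MMRM, Toeplitz | Same (8.1.3, 12) | Not needed |
| Biomarkers | ANCOVA | ANCOVA, with the Phase B reference moved to baseline | Yes |

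The similarity clause in 10.4.4 held for Pain NRS and did not hold for the other outcomes that the protocol models by MMRM.

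**The case against.** **Phase B is openly secondary.** No formal hypothesis test is planned (Protocol 10.2), Phase A is the primary analysis, and the SAP calls Phase B complementary and gives it no estimands. This stands. A reader might infer that type I error is inflated; the documents allocate no alpha to Phase B, so they do not support that.

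**The methods were not wholly open.** The protocol lists the Phase B endpoints, gives models and covariance structures for Phase A and carries them forward in general terms. That protocol is dated 21 August 2020. With last completion estimated for October 2021, the last Week 52 visit falls about October 2020, so the clause probably predates unblinding (an inference). Investigators and subjects stayed blinded, and deviations were reviewed before the Phase B lock. All of this stands as constraint, but step 4 shows that it did not fix the methods.

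**Past tense dates the final text, not the decisions.** This also stands. The Phase A SAP is not among the documents, so some departures may have been settled there before unblinding. A reader might infer that methods were chosen because of the Phase A results; nothing supports that. A neutral reason is easy to see for WOMAC. An unstructured matrix over 26 monthly visits has 26 × 27/2 = 351 parameters, against 13 × 14/2 = 91 over the 13 visits of Phase A. The same reason is weaker for qCT (8 × 9/2 = 36) and mJSW (4 × 5/2 = 10).

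**Other readings that go too far.**
- That the Sponsor had also seen Phase B data by arm when it wrote the SAP: the documents describe only a Phase A analysis at that unblinding.
- That the Phase A analysis should have been called interim: relabelling it would not have fixed any Phase B method.
- That losing the deadline in the Amendment 03 log ("A second SAP will be prepared for Phase B analyses and finalized prior to the Week 104 data lock") is itself an error: that text is superseded, and its milestone would not have placed the SAP before the Phase A unblinding.

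**Conclusion.** The point holds as a cheap improvement. The current protocol let the Phase B methods be settled with treatment codes known, and the SAP's text indicates that it was finalised in that state. At least half of every Phase B model's time points lie in Phase A. Four groups of departures from the protocol's methods are undeclared, against one change that is declared.

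The consequence is limited to the credibility of the Phase B bone imaging, efficacy and biomarker estimates and the intervals and P values reported with them. The adverse event, vital sign and laboratory summaries are descriptive, with no model to select, and are unaffected. No bias in any result is shown.

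The conclusion rests on the SAP's tense and content in place of a visible date, and on reading Protocol 10.4.4 as carrying the methods of 10.4.2-10.4.3 forward to Week 104.

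**What to change.** The protocol should have required the Phase B SAP to be signed before Phase A treatment codes were released. That can no longer be met here. For the present SAP:

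1. Make the Protocol 10.4.2-10.4.3 methods, extended to Week 104, the default Phase B analysis. This restores the target-knee BMD MMRM, the BMD ratio with its one-sided interval, the MMRMs for WOMAC, Patient Global Assessment and mJSW, and the durability models. Name a fallback covariance structure for the monthly outcomes in case the unstructured matrix cannot be fitted; Toeplitz is already used for Pain NRS.
2. State in SAP 15 the SAP's sign-off date relative to the Phase A unblinding.
3. List in SAP 15 every departure from those methods, marked as decided after unblinding unless an earlier document shows otherwise. Where the Phase A SAP already made the change, cite it.

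Cost: some models to run or re-run from specifications that the protocol already contains, and a short addition to SAP 15. The downside is a post hoc label on some analyses. Sample size and power do not change.

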10.2 STATISTICAL HYPOTHESES

No formal hypothesis test will be performed in this study.

10.3 ANALYSIS DATASETS

Full Analysis Set (FAS): All subjects who are randomized and receive at least one study injection. Full analysis set is used to describe the analysis set which is as complete as possible and as close as possible to the intent-to-treat ideal of including all randomized subjects.

Modified Full Analysis Set (mFAS): FAS subjects who received injections into the target knee both on Day 1 and at Week 24.

Per-Protocol Analysis Set (PPAS): mFAS subjects who complete the study and do not have any protocol deviations that may impact the evaluation of efficacy outcomes.

Safety Analysis Set (SAS): All subjects who receive at least one study injection.

10.4 DESCRIPTION OF STATISTICAL METHODS

10.4.1 GENERAL APPROACH

For continuous variables, the number of subjects in the analysis, mean, standard deviation (SD), median, minimum, and maximum will be reported. All categorical endpoints will be summarized using frequencies and percentages. The principal analysis of the Phase A endpoints will be conducted on data extracted from the study database after the last subject completes the Week 52 (EOSa) visit.

10.4.2 ANALYSIS OF PHASE A GENERAL SAFETY AND BONE IMAGING ENDPOINTS

The number and percent of subjects experiencing AEs in Phase A will be summarized by seriousness, severity, and relationship for each treatment group.

Change over time in BMD in the target knee as assessed by qCT will be characterized using a mixed-effects model for repeated measures (MMRM) in order to estimate change from baseline with treatment group, week, treatment×week, and baseline as covariates. The model will be evaluated at Week 52. Unadjusted 95% confidence intervals and P values will be reported. The model will be estimated assuming an unstructured variance-covariance matrix, allowing the data to fully inform the correlation between within-subject observations ([Kincaid 2005](#)).

As a sensitivity analysis, analysis of covariance (ANCOVA) will be used to estimate baseline-adjusted BMD in the target knee at Weeks 12, 24, 36, and 52. The ratio of baseline-adjusted BMD between SM04690 and placebo will be presented with a one-sided 95% confidence interval.

Baseline-adjusted ANCOVA will also be used to analyze the within-subject difference in BMD between the target and non-target knee by qCT for SM04690, within-subject difference in BMD between the target and non-target knee by qCT for placebo, and change from baseline in BMD of the spine and hips by DXA for SM04690 subjects versus placebo. The models will be adjusted for baseline and evaluated at Weeks 12, 24, 36, and 52 for qCT and Weeks 24 and 52 for DXA. Unadjusted 95% confidence intervals and P values will be reported.

10.4.3 ANALYSIS OF PHASE A EFFICACY AND EXPLORATORY BIOMARKER ENDPOINTS

Changes in the target knee from baseline in Pain NRS, WOMAC Function, WOMAC Pain, mJSW, and Patient Global Assessment will be characterized using MMRM; the models will be evaluated through Week 52. All models will use treatment group, week, treatment×week

interaction, and baseline values as covariates. Unadjusted 95% confidence intervals and P values will be reported.

For WOMAC, mJSW, and Patient Global Assessment, the model will be estimated assuming an unstructured variance-covariance matrix. For Pain NRS, the model will be estimated assuming a Toeplitz variance-covariance matrix. The Toeplitz structure is a more generalized form of autoregressive-1 structure, allowing the data to inform how the correlation between within-subject observations decreases over time instead of implicitly defining a uniform decay structure (Kincaid 2005).

To assess response durability, changes in the target knee from Week 24 (i.e., after second injection) in Pain NRS, WOMAC Function, WOMAC Pain, mJSW, and Patient Global Assessment will be characterized using MMRM; the models will be evaluated through Week 52. All models will use treatment group, week, treatment×week interaction, and Week 24 values as covariates. Unadjusted 95% confidence intervals and P values will be reported.

Baseline-adjusted ANCOVA will be used to analyze the change from baseline in serum bone biomarkers (e.g. PINP and β -CTX) and a serum cartilage biomarker (e.g., COMP) for SM04690 subjects versus placebo. The models will be adjusted for baseline and evaluated at Weeks 4, 12, 24, 36, and 52. Unadjusted 95% confidence intervals and P values will be reported.

